1.2 Secondary Objectives

- To evaluate the safety and tolerability (in terms of Rituxan-related adverse events) in patients with melanoma receiving CCB.
- To compare objective response rate in patients receiving CCB therapy + Rituxan versus CCB therapy alone.
- To compare 1 year overall and progression-free survival in patients receiving CCB therapy + Rituxan versus CCB therapy alone.
- To compare changes in CD21^{lo} B cells in patients receiving CCB therapy + Rituxan versus CCB therapy alone.
- To compare changes in T cells in patients receiving CCB therapy + Rituxan versus CCB therapy alone.

Exploratory Objectives

• To compare treatment induced changes in tumor tissue in patients receiving CCB therapy + Rituxan versus CCB therapy alone.

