5.3 Duration of Follow Up

Patients will be followed for 4 weeks after removal from study or until death, whichever occurs first. Patients removed from study for unacceptable adverse event(s) will be followed until resolution or stabilization of the adverse event.

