5.4 Criteria for Removal from Study

Patients will be removed from study when any of the criteria listed in Section 5.2 applies. The reason for study removal and the date the patient was removed must be documented in the Case Report Form.

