12.1.6 Progression-Free Survival

PFS is defined as the duration of time from start of treatment to time of progression or death or last follow-up, whichever occurs first.

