14. STATISTICAL CONSIDERATIONS

14.1 Study Design/Endpoints

Endpoints:

Primary:

• Primary endpoint is the rate of CTC (v5.0) grade 3 or greater immune-related adverse events at 6 months of follow up.

Secondary:

- Rate of CTC (v5.0) toxicity related to Rituxan.
- Objective tumor response as assessed by RECIST v1.1 and irRECIST at 12 weeks and every 12 weeks thereafter.
- Rates of overall and progression-free survival at 1 year following initiation of therapy.

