14.2 Sample Size/Accrual Rate

This is an open-label, 2-arm phase II clinical trial to study the differential effect in the risk of IRAEs between treatment and control groups. A sample size of 22 patients per arm (44 total) will provide us approximately 80% power to detect a 40% difference in the rates of developing ≥grade 3 IRAE within 6 months follow up between the control and the treatment arm (estimated to be 60% in the control arm, Callahan et al; J Clin Oncol. 2017 Dec 1;35(34):3815-3822). The sample size calculation is based on Fisher's exact test at a one sided significance level of 0.05 under the following assumptions: 1). Patients will be randomized in 1:1 ratio of the treatment to control arm. 2). Approximately 60% patients in the placebo arm will develop > grade 3 IRAE

within 6 months based on our pilot study. 3). The treatment will reduce the rate of ≥ grade 3 IRAE to 20% in the treatment arm. In a recent study, the rate of objective response following combination checkpoint blockade was 42% (Callahan et al; J Clin Oncol. 2017 Dec 1;35(34):3815-3822). In order to monitor potentially adverse impact of Rituxan on checkpoint blockade, we will utilize early stopping rules based on an adaptive design wherein trial will be stopped if we have strong evidence of rates of objective response of <30%. The trial will be stopped early in the unlikely event that less than 2 patients among the first 12 patients treated by Rituxan respond to therapy. If the rate of objective response is > 30%, the probability that at least two out of first twelve patients will achieve an objective response of at least a PR for the first 12 patients is approximately 92%. Hazard ratios and corresponding two-sided 95% confidence intervals will be estimated using Cox-proportional hazards model, with the treatment group as a single covariate. Progression-free and overall survival curves, median with 95% confidence intervals, and progression-free survival rates at 6 months will be estimated with the use of Kaplan-Meier method. Biostatistics support for the study will be provided by biostatistics core resource of Winship Cancer Center.

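### Section 14.2 names a 6-month PFS rate although the secondary endpoint is 1-year PFS and OS, and the follow-up sections conflict on whether every patient is followed to 1 year

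*Combined protocol and SAP*

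**What the plan says.** **Objective and endpoint.** The secondary objective in Section 1.2 is: "To compare 1 year overall and progression-free survival in patients receiving CCB therapy + Rituxan versus CCB therapy alone". The matching endpoint in Section 14.1 is: "Rates of overall and progression-free survival at 1 year following initiation of therapy".

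**Analysis.** The survival analysis is two sentences in Section 14.2. The first plans a Cox model: "Hazard ratios and corresponding two-sided 95% confidence intervals will be estimated using Cox-proportional hazards model, with the treatment group as a single covariate". The second plans "Progression-free and overall survival curves, median with 95% confidence intervals", and then adds that "progression-free survival rates at 6 months will be estimated with the use of Kaplan-Meier method".

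**PFS definition (Section 12.1.6).** "PFS is defined as the duration of time from start of treatment to time of progression or death or last follow-up, whichever occurs first".

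**Follow-up.** Section 5.3 states: "Patients will be followed for 4 weeks after removal from study or until death, whichever occurs first". Patients removed for unacceptable adverse events are followed until the event resolves or stabilises. Section 5.4 states: "Patients will be removed from study when any of the criteria listed in Section 5.2 applies". Disease progression is one of the Section 5.2 criteria.

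**Text pointing to longer follow-up.** The post-study item in Section 7.2 asks investigators, in studies that collect survival data, to report deaths from any cause after the adverse event reporting period. Footnote b of the Section 11 calendar schedules CT every 12 weeks for two years and less often after that.

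**The concern.** The only fixed-time survival rate that the analysis text names is at a time, and for an outcome, that no objective or endpoint asks for. The 1-year rates that the protocol does ask for are not named, and no method is given for comparing them at 1 year. In an open-label trial this leaves the reported landmark, 6 months or 1 year, open to choice after the data are seen.

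Follow-up makes this more than a slip of wording. If patients leave follow-up shortly after progression, OS is censored in the patients most likely to die next. Kaplan-Meier and Cox methods both assume that a censored patient has the same future risk as those still observed. Here that would fail, and 1-year OS would tend to be overstated. If the arms differed in progression, the OS comparison would be distorted too: an arm with more progression would lose more of its later deaths.

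Section 2.4 says that preventing immune-related adverse events is worthwhile only if tumour control and its durability are not harmed. One-year PFS and OS bear directly on durability.

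**Working it through.** **1. The plan's own figures.** No survival rate, event count or survival power is stated, so there is no survival figure to reproduce. The only power figure is for the primary endpoint: 22 per arm, 60% versus 20%, Fisher's exact test, one-sided 0.05, about 80%. Full enumeration gives 79.1%, which agrees. Nothing below touches that calculation.

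**2. Endpoint against analysis.**

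| Item | Sections 1.2 and 14.1 | Section 14.2 |
|---|---|---|
| PFS rate | 1 year | 6 months |
| OS rate | 1 year | none at any time |
| Comparison between arms | at 1 year (Section 1.2) | Cox hazard ratio over all follow-up; none at a fixed time |
| Curves and medians | not mentioned | PFS and OS |

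Elsewhere in Sections 1.1 and 14.1, 6 months is the window for the primary toxicity endpoint. It is not attached to PFS in any objective or endpoint.

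**3. Can a 1-year value be obtained?** Yes, from the planned curves, if patients are observed for 1 year. Imaging supports this for PFS: a 12-weekly schedule gives scans at weeks 12, 24, 36 and 48 within 52 weeks.

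**4. Does follow-up reach 1 year?** Chain Sections 5.2, 5.4 and 5.3: progression is a listed criterion, a listed criterion leads to removal, and removal is followed by 4 weeks of follow-up. On that reading, a patient who progresses at the week-12 scan is followed to week 12 + 4 = 16, which leaves 52 − 16 = 36 weeks of the first year outside follow-up. PFS is unaffected for that patient, because the event has already occurred; OS is affected. A patient removed for another reason, such as withdrawal or intercurrent illness, could be lost to both.

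Three passages conflict with this reading or leave it open:
- Section 5.2 is written around the four weekly rituximab doses (or observation), which the calendar places in weeks 2 to 5. Whether progression at week 12 still triggers removal is not stated.
- The post-study item in Section 7.2 asks for all deaths, but gives no contact schedule and no end date. The reporting-period text in the same section limits later reports to serious events attributed to study treatment.
- The Section 11 footnote schedules CT well beyond 1 year.

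**5. Precision once 1 year is named.** Assumptions: 22 per arm, no censoring before 1 year, the same true rate S in both arms, S from 30% to 80%. Without censoring the Kaplan-Meier estimate is a simple proportion.

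- Per-arm 95% half-width: 1.96 × √(S(1 − S)/22)
- Half-width for the difference: 1.96 × √(2S(1 − S)/22)

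| S | Per arm | Difference |
|---|---|---|
| 0.30 | 0.191 | 0.271 |
| 0.50 | 0.209 | 0.295 |
| 0.80 | 0.167 | 0.236 |

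That is about 17 to 21 points per arm and about 24 to 30 points for the difference. Earlier censoring would widen both.

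**The case against.** The strongest reply is that little is lost. The sentence that names 6 months also plans full PFS and OS curves, and the sentence before it plans hazard ratios by arm. A 1-year value can be read from a curve, and the arms are compared. This stands, and it rules out the stronger reading that a reader might infer, namely that the plan cannot produce its endpoint. It does not supply a named 1-year rate or a comparison at 1 year, and it depends on follow-up reaching 1 year.

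A second reply is that Section 7.2 asks for all deaths and Section 11 keeps scanning for years. This also stands in part. A reader of Section 5.3 alone might infer that deaths after progression are simply not seen; the documents do not support that as a flat statement. What they show is a conflict: one section states a follow-up duration, and the others imply longer observation without a schedule for vital status.

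A third reply is that objective response rate is the outcome monitored for harm to efficacy, with stopping rules in Section 14, and that 22 per arm is too few for a useful 1-year comparison. Both observations are fair. Response rate does not measure survival, however, and imprecision is a reason to report the interval, not to leave the stated endpoint out of the analysis.

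**Conclusion.** The mismatch is certain on the text: Section 14.2 specifies a 6-month PFS rate that no objective or endpoint calls for, and omits the 1-year PFS and OS rates and the 1-year comparison.

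The follow-up part is conditional. If Sections 5.2 to 5.4 are applied as in step 4, OS is censored informatively from 4 weeks after progression, and the 1-year OS estimate would be biased, most likely upward. If the Section 7.2 and Section 11 text governs in practice, the bias may be small. The size cannot be calculated, because the documents give no progression or death rates.

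Only secondary endpoints are affected; the primary endpoint, the 44 patients and the power of about 80% stand. The change should be made, but it does not put the main analysis in doubt.

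**What to change.** **Section 14.2.** Replace the 6-month PFS rate with Kaplan-Meier PFS and OS rates at 1 year for each arm, and the between-arm difference in each, all with 95% confidence intervals. Keep the curves, medians and hazard ratios. Six-month PFS may stay if it is labelled as an additional summary.

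**Sections 5.3 and 5.4.** Reconcile these with the post-study item in Section 7.2 and the imaging footnote in Section 11. State that vital status, and progression where not yet documented, are collected to 1 year from the start of therapy for every randomised patient, regardless of removal from study treatment. This concerns data collection only; the criteria for stopping treatment need not change.

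**Cost.** A wording amendment and vital-status checks to 1 year. CT every 12 weeks over that period is already scheduled. Sample size and primary power are unchanged. The remaining drawback is the imprecision shown in step 5, which the report should state.

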The discovery that patients who experience early changes in B cells following CCB therapy are at higher risk for subsequent development of IRAEs provides the opportunity to prevent IRAEs in this cohort. These studies will test a novel strategy of B cell depletion to reduce the risk of autoimmunity following combination checkpoint blockade. This is feasible because CCB-emergent changes in B cells not only precede autoimmune complications but are also directly amenable to targeting via anti-CD20 antibodies. It is important to note that even if this approach does not work clinically, it will provide biologically and clinically important information. For example, it would then suggest a role of other immune cells in mediating IRAEs. Recent studies have suggested that B cell depletion may also enhance anti-tumor effects in melanoma and therefore this combination may not only reduce toxicity but also improve efficacy(19).

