2.4 Correlative Studies Background

CD21^{lo} B cells as targets in IRAEs following combination checkpoint blockade:

Our studies are also among the first to identify a role for CD21^{lo} subset of B cells in CCB-induced IRAEs. Our preliminary data indeed identified this as a specific subset of human B cells that express PD1. Improved understanding of the biology of this specific B cell subset in melanoma patients and changes in these cells following CCB will therefore provide novel mechanistic insights into CCB-induced IRAEs. These studies may also suggest novel approaches to specifically target this specific subset, as opposed to the current strategy targeting all B cells to lower the risk of IRAEs.

Contributions of B cells to protective immunity mediated by combination checkpoint blockade:

While the role of T cells in protective immunity is well established, the relative contribution of B cells to the anti-tumor effects of checkpoint blockade remain to be clarified, particularly in human studies. In preclinical models, depletion of B cells did not lead to reduction in anti-tumor effects of checkpoint blockade(19). The application of B cell depleting antibody with Rituxan in patients undergoing CCB will provide direct and novel insights into the role of B cells in both IRAEs and tumor immunity. The latter is particularly relevant because approaches targeting IRAEs will only be clinically viable if they do not adversely impact protective tumor immunity or alter the frequency or durability of clinical tumor regressions following CCB therapy.

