12.1.1 Definitions

Evaluable for toxicity. All patients will be evaluable for toxicity from the time of their first treatment with ipilimumab/nivolumab.

Evaluable for objective response. Only those patients who have measurable disease present at baseline, have received at least one cycle of therapy, and have had their disease re-evaluated will be considered evaluable for response. These patients will have their response classified according to the definitions stated below. (Note: Patients who exhibit objective disease progression prior to the end of cycle 1 will also be considered evaluable.)

Evaluable Non-Target Disease Response. Patients who have lesions present at baseline that are evaluable but do not meet the definitions of measurable disease, have received at least one cycle of therapy, and have had their disease re-evaluated will be considered evaluable for non-target disease. The response assessment is based on the presence, absence, or unequivocal progression of the lesions.

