Newly diagnosed patients as well as patients that have previously received anti-PD-1 therapy in adjuvant setting will be randomized as separate groups equally between the two arms. This will allow us to normalize the ORR between the two groups. ORR will be calculated for every 10 patients enrolled. The trial will be stopped early if there is a difference in ORR of greater than 30% between the two arms.

REFERENCES

- 4. Wolchok JD. PD-1 Blockers. Cell. 2015;162(5):937.

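### The stop for an ORR difference above 30% names no direction and no stopping probability, and the stated 80% power ignores it

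*Combined protocol and SAP*

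**What the plan says.** The last two sentences of Section 14.2 set the rule. On timing: "ORR will be calculated for every 10 patients enrolled". On action: "The trial will be stopped early if there is a difference in ORR of greater than 30% between the two arms". Neither sentence gives a direction, a minimum number of evaluable patients or a probability of stopping.

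The same section explains why response is monitored: "In order to monitor potentially adverse impact of Rituxan on checkpoint blockade, we will utilize early stopping rules based on an adaptive design". That sentence leads into a different rule, a stop if fewer than 2 of the first 12 Rituxan patients respond. For that rule the plan does give an operating characteristic, a 92% chance of at least 2 responders when the ORR is 30%.

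The sample-size statement reads "A sample size of 22 patients per arm (44 total) will provide us approximately 80% power". It rests on a one-sided Fisher exact test at 0.05, for grade 3 or higher IRAE rates of 60% v 20%, and does not mention interim stopping.

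The background points both ways on direction. Section 2.4 holds that "approaches targeting IRAEs will only be clinically viable if they do not adversely impact protective tumor immunity"; Section 2.3 suggests that "this combination may not only reduce toxicity but also improve efficacy".

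Section 12.1.1 defines who is evaluable for response: "Only those patients who have measurable disease present at baseline, have received at least one cycle of therapy, and have had their disease re-evaluated". It adds that "Patients who exhibit objective disease progression prior to the end of cycle 1 will also be considered evaluable". Sections 11 and 14.1 place the first response assessment at 12 weeks.

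**The concern.** Three things are left open.

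- **Direction.** The aim is to catch harm to tumour response, but the rule is triggered by any difference. Taken at its word, it ends the trial when Rituxan has the better response.
- **Who counts at a look.** Looks are set by enrolment, while a patient's response is first known at 12 weeks. The rule is not tied to the evaluability definition, does not say whether looks are cumulative, and does not say how a patient who dies or deteriorates before re-evaluation is counted.
- **Operating characteristics.** No stopping probability is given, the stated power ignores the rule, and the plan does not say whether the primary endpoint is tested after a stop.

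At 5 v 5, a gap of two responders is 2/5 = 40 points and stops the trial. A safeguard meant for harm can therefore end the study by chance before the planned 22 v 22 IRAE comparison, and neither the DSMC nor a reader is told how often.

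**Working it through.** **Inputs from Section 14.2.** ORR 42%; looks at 10, 20, 30 and 40 enrolled; 22 per arm; one-sided Fisher at 0.05; IRAE 60% v 20%.

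**Assumptions.** The 30% means absolute percentage points and must be strictly exceeded. Looks are cumulative with equal arms. True ORR is 42% in both arms. IRAE is independent of response.

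**Step 1: the plan's own figures.** Enumerating two binomials, Fisher power at 22 v 22 is 0.791, which matches the stated 80% only if all 44 patients are analysed with no early stop. For the other rule, P(at least 2 of 12 | 0.30) = 0.915, matching the stated 92%.

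**Step 2: first look at 5 v 5.** For Bin(5, 0.42), the probabilities of 0 to 5 responders are 0.0656, 0.2376, 0.3442, 0.2492, 0.0902 and 0.0131. The chance that control leads by at least 2 is

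0.3442×0.0656 + 0.2492×0.3032 + 0.0902×0.6474 + 0.0131×0.8966 = 0.168.

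Either direction: 0.337.

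**Step 3: all looks.** Exact recursion over responder counts, carrying forward only trials not yet stopped:

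| First look | Lower Rituxan ORR only | Either direction |
|---|---|---|
| 5 per arm (then 10, 15, 20) | 0.1683 + 0.0134 + 0.0119 + 0.0018 = 0.196 | 0.3366 + 0.0269 + 0.0234 + 0.0036 = 0.391 |
| 10 per arm (then 15, 20) | 0.0552 + 0.0203 + 0.0028 = 0.078 | 0.157 |

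With equal true response every one of these stops is chance. In the first row the first look supplies 0.1683/0.1955 = 86% of them. With a 5 v 5 first look and a common ORR of 30% to 50%, the ranges are 17% to 20% (lower-only) and 34% to 40% (either direction). Simulating blocks of 6 (Section 5.1) gives 21% and 42% at an ORR of 42%.

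**Step 4: power with the rule included.** Fisher power at 5, 10, 15 and 20 per arm is 0.142, 0.425, 0.599 and 0.753. For lower-only with a 5 v 5 first look:

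- No claim after a stop: (1 − 0.1955) × 0.791 = 0.637.
- Tested at the stop: 0.637 + 0.1683×0.142 + 0.0134×0.425 + 0.0119×0.599 + 0.0018×0.753 = 0.675.
- Five more patients per arm already enrolled and followed: 0.637 + 0.1683×0.425 + 0.0134×0.599 + 0.0119×0.753 + 0.0018×0.791 = 0.726. With ten more per arm: 0.758. The plan gives no accrual rate, so the overrun is an assumption.

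The corresponding literal-reading figures are 0.482, 0.558 and 0.662 to 0.726.

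For lower-only with a first look at 10 per arm:

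- No claim: (1 − 0.0783) × 0.791 = 0.729.
- Tested at the stop: 0.729 + 0.0552×0.425 + 0.0203×0.599 + 0.0028×0.753 = 0.767.

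**Step 5: what naming the direction costs.** Simulation with blocks of 6 and the 2-of-12 rule included, at an assumed true ORR of 42% v 25%. The literal rule stops 0.442 (Rituxan lower) + 0.064 (Rituxan better) + 0.048 (2-of-12) = 0.554 of trials. Lower-only stops 0.443 + 0.047, about 0.49. Stops for low Rituxan response are 0.49 either way. At an assumed 42% v 15%, they are 0.73 either way.

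**The case against.** The strongest reply is that the 20% depends on a first look the schedule may not deliver. When the tenth patient enrols, ten patients will not normally have a 12-week assessment. If the first usable comparison has 10 per arm, chance stopping falls to about 8%, or 16% read literally. This stands, and any figure has to carry its look size. It also shows the gap: the plan does not say what a look contains.

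Second, the direction can be inferred. Section 14.2 speaks of early stopping rules in the plural and gives adverse impact as their purpose. A reader might conclude that the trial really faces 39% chance stopping and 48% power. The documents do not support that as the expected behaviour: it takes the wording at its most literal and, for the power, assumes that a stopped trial makes no primary claim, which no section says. Those figures are a worst case. The sentence itself still names no direction.

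Third, the power loss may be modest. Nothing in the plan pauses accrual while scans are awaited, so some overrun is plausible; with 5 to 10 more patients per arm, lower-only power is 73% to 76% against 79%.

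Fourth, independence of IRAE and response is untested. Section 2.3 links higher response to more grade 3-4 IRAEs across regimens. The power figures are therefore illustrations. A reader might also infer that the rule inflates the type I error of the IRAE test; under independence it does not.

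Finally, Section 12.1.1 already defines evaluability. What remains is to tie the rule to it and to deal with patients never re-evaluated.

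**Conclusion.** The concern holds in a limited form and should be fixed. The rule as worded would stop the trial for a better Rituxan response, contrary to the monitoring aim, and the stated power takes no account of it. If a stop can occur with fewer than 22 per arm enrolled, or if no primary test follows it, the 79.1% is not delivered.

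The size depends on the first look. With 42% ORR in both arms and cumulative looks, chance stopping under the lower-only reading is about 20% from a 5 v 5 first look and about 8% from 10 v 10. Under independence of IRAE and response, lower-only power is 64% to 76% in the first case, depending on testing after a stop and on overrun up to 10 per arm. In the second it is 73% to 77%, from no claim to testing at the stop.

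A reader might take the 20% as the trial's established false-stopping rate. The documents do not fix the look size, so it is a conditional figure. The gap in the wording is certain; the number is not.

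**What to change.** Rewrite the last two sentences of Section 14.2.

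1. State that only a lower ORR in the Rituxan arm counts, in line with the section's own aim. This removes only the stops where Rituxan looks better and loses essentially no protection against low Rituxan response (step 5).
2. Define each look by response-evaluable patients as in Section 12.1.1 and say that looks are cumulative. State how patients who die or deteriorate before re-evaluation count, so that they are not dropped from the harm monitor. As an illustration at an assumed 42% v 25%: if 20% of Rituxan patients are never re-evaluated and are left out, the evaluable Rituxan ORR becomes 0.25/0.80 = 31%, and lower-only stopping falls from 43% to 33% (equal arms, without the 2-of-12 rule).
3. Give the stopping probabilities, say whether the primary endpoint is tested after a stop, and restate the power with the rule included.

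The cost is protocol wording and a short table, with no extra patients; looks tied to evaluable patients come later. These changes disclose the remaining chance stopping, about 20% with a 5 v 5 first look, and do not remove it.

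Two further options would reduce automatic stops, but they are trade-offs for the sponsor. One is to make a crossing a trigger for DSMC review, with ORR by arm added to the review materials listed in Section 13.1.2. The other is to drop the 10-patient look, which would cut stopping for low Rituxan response (both rules) from about 49% to 37% at 42% v 25%, and from about 73% to 66% at 42% v 15%. The 25%, 15% and 20% values are assumptions, not plan figures.
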